Appendix 1 – Schedule of Study Activities

	Baseline	18-24 hours (after randomization)	48-96 hours (after randomization)	30-day Follow-Up	90-day Follow-Up
Informed Consent	X				
Review Medial History	X				
Review Medication History	X				
Height and Weight	X				
Vital Signs ^a	X	X	X		
Echocardiogram (TTE)	X	X	X		
Electrocardiogram (ECG)	X	X	X		
Hemodynamics ^b	X	X	X		
Blood Tests ^c	X	X	X		
Vasoactive Medication Dosing		X			
Potassium (pts randomized to cooling)		Q 4 hours			
Glucose Checks (pts randomized to cooling)		Q 1 hour			
Urine Output	X	X	X		
Randomization	X				
Adverse Events		X	X	X ^d	X ^d

^a blood pressure, heart rate, temperature (bladder or esophageal), respiratory rate

^b RA pressures, RV pressures, PA pressures, pulmonary capillary wedge pressure (PCWP), Fick cardiac output and cardiac index, systemic vascular resistance (SVR), pulmonary vascular resistance (PVR), cardiac power and cardiac power index, mixed venous saturation (MVO2)

^c serum lactate level, basic metabolic panel, hepatic function, coagulation parameters, complete blood count (CBC), arterial blood gas (ABG), and optional blood samples for future research

^d to be completed in clinic, when possible, or by phone

^e items to be charged to research during cooling include: meperidine

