Patients with cardiogenic shock, regardless of the underlying etiology, present with hypotension, shortness of breath, altered mental status, signs of volume overload (elevated jugular venous pressure, pulmonary rales, lower extremity edema), and evidence of end-organ hypoperfusion. These patients are typically admitted to the Coronary Care Unit (CCU) for aggressive treatment to reverse the course of the disease. Standard of care therapy for these patients involves initiation of ionotropes and/or vasopressors along with diuretics. Often, mechanical circulatory support (i.e. Intra-arterial balloon pump or temporary left-ventricular assist devices) and invasive hemodynamic monitoring (i.e. placement of a pulmonary artery catheter) is necessary.

The results of the small trials mentioned above are encouraging, but larger randomized trials are necessary to establish the role of TH in patients with cardiogenic shock. We propose a first-ever randomized clinical trial to prospectively study the effects of TH in patients with cardiogenic shock. In addition to assessing the safety of TH in this patient population, hemodynamic parameters, echocardiographic assessment of cardiac function during hypothermia, as well electrocardiographic changes with hypothermia will be studied. The echocardiographic changes during TH have never been previously reported. Studying TH in patients with cardiogenic shock is important, as therapies for this highly morbid condition have remained largely unchanged for many years. Given the high mortality associated with cardiogenic shock despite advances in medical and mechanical support, the clinical implications of results from this trial may be large.

Objective

The purpose of the study is to prospectively randomize patients with cardiogenic shock to standard therapy plus therapeutic hypothermia or standard medical therapy alone in order to assess the safety of TH in patients with cardiogenic shock. This study will also help understand the physiologic effects of TH in cardiogenic shock. This will be a pilot study to establish the safety of TH and to assess tolerability of TH in this patient population.

Methods

A. Patient Population:

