5. TTE
6. Blood sample for future research

Endpoints

Primary safety endpoints:

1. Arrhythmia requiring medical therapy or therapy with temporary pacemaker
2. Bleeding requiring transfusions as a direct result of the cooling catheter insertion or secondary to resulting coagulopathy
3. Clinically important bloodstream infection, as confirmed with 2 positive blood cultures, or suspected sepsis in the absence of positive blood cultures with a sequential organ failure assessment (SOFA) score >2
4. Hypokalemia with potassium levels below 3.0mEq/L, not secondary to other identifiable causes

Secondary endpoints:

1. Hemodynamic changes during intervention period – Cardiac output/Cardiac Index, PCWP, SVR, mixed venous oxygen saturation (MVO₂), cardiac power index
2. Cumulative vasopressor and inotrope dose requirements (i.e. number of vasoactive and/or inotropic drugs used)
3. Echocardiographic % change in ejection fraction at 18-24 hours (from baseline)
4. In-hospital all-cause mortality

Procedures

Patients admitted to the Coronary Care unit (CCU) at the University of Chicago will be screened by the study investigators and the cardiology fellow on the CCU rotation. Patients meeting the inclusion criteria, as defined previously, will be identified and randomized after informed consent within 12 hours of presentation. Patients will be randomized to either TH plus standard medical care or to standard medical care alone. A pulmonary artery (PA) catheter will be placed at the bedside or in the Cardiac Cath lab if difficult anatomy is anticipated. As mentioned earlier, placement of a PA catheter is part of the standard of care for management of cardiogenic shock. Currently, patients who are admitted to the University of Chicago CCU with cardiogenic shock routinely undergo placement of PA catheter by the cardiology fellow in the CCU or in the cardiac cath lab. Data from the PA catheter is vital in initiating vasopressors/inotropes, assessing the response to the therapies, and possible need for escalation of therapy (i.e. mechanical support). In this study, patients in each arm will undergo PA catheter placement.

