Hyperglycemia is common during TH as lower temperatures decrease insulin secretion and increase insulin resistance. Many patients with heart failure and cardiogenic shock have concomitant diabetes and glucose control can often be difficult to achieve in these critically ill patients. Clinically significant hyperglycemia will be defined as glucose level exceeding 200mg/d requiring continuous insulin infusion in patients without a diagnosis of diabetes mellitus. Hyperglycemia in patients with diagnosis of diabetes mellitus, or hyperglycemia as a result of other identifiable causes (i.e. administration of steroids, adrenal derangements) will not be considered as a result of TH. In patients who develop hyperglycemia requiring continuous insulin infusion as a direct result of TH, the patient will be treated expectantly and hyperglycemia will be recorded as an adverse event. During TH period, blood glucose will be measured at least hourly during TH, especially in patients receiving intravenous insulin, and during rewarming, when glucose levels can fall.

Hypothermia will lower serum potassium levels, primarily by promoting inward cellular potassium flux, although hypothermia also induces a mild diuresis with concurrent electrolyte wasting. Serum electrolytes will be measured at regular intervals (every 4–6 hours). Potassium will be repleted to maintain levels above 3.5 mEq/L. Rewarming reverses the potassium flux and increases serum levels, so repletion will be held 4 hours before rewarming begins. Clinically significant hyperkalemia is unusual in patients with preserved renal function. In patients with hypokalemia not due to other identifiable causes (diuretic administration, adrenal derangements, etc.), potassium supplements will be administered as per standard of care. Hypokalemia with potassium levels below 3.0mEq/L not secondary to other identifiable causes in patients undergoing TH will be considered an adverse event.

The target temperature of 32-34°C will be achieved using the intravascular cooling catheters. The body temperature will be recorded every 1-2 hours as per the CCU policy in the TH group (as well as the control group). The time spent in the therapeutic window will be recorded and reported. Any deviations outside of the range, specifically $<32^{\circ}\text{C}$ lasting >5 minutes will be reported as an adverse event.

Mitigating Risks associated with cooling catheter insertion:

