The risks associated with insertion of a cooling catheter are the same as insertion of any central lumen catheter. These include, but are not limited to, bleeding, infection, and vascular injury. Previously published studies have quoted risk of localized hematomas at 4.7% and risk of vascular injury (most frequently due to inadvertent arterial puncture) at $<1\%$.²³ Incidence of line-associated blood stream infection has been reported as 80-189 episodes per 100,000 patient years.²³

Insertion of a central venous catheter is standard of care in patients in cardiogenic shock to allow for administration of inotropes/vasopressors. The ZOLL Quattro catheters include three standard

central venous catheter infusion lumens to allow for administration of these vasoactive medications. Therefore, patients randomized to TH arm will not need an additional central venous line. Rather, insertion of a cooling catheter will serve the purpose of initiation and maintenance of TH while also allowing for administration of drugs via the infusion lumens. The risk associated with cooling catheter insertion is not expected to be higher than insertion of a standard central venous line.

C. Monitoring of Safety:

During the intervention period, participants will be monitored by physicians, nurses, and technicians in accordance with standard medical care. This includes 24-hour monitored telemetry, with measurement of heart rate, blood pressure, oxygen saturation, and respiratory rate. Real-time hemodynamic monitoring will be measured using pulmonary artery catheters. Blood glucose and electrolyte measurements will be performed as per protocol for patients undergoing therapeutic hypothermia, and correction of abnormalities will be performed by the treating team. Shivering will be monitored by the treating nurse, per ICU protocol, and will be reported to the treating team. TH will not influence the clinician's medical decisions – any medical or mechanical intervention necessary based on clinical status will be allowed.

D. Data Safety Monitoring Board:

Adverse events will be reviewed by the Data Safety Monitoring Board as described below. The study will be halted upon the discovery of unanticipated adverse device events that present a significant or unreasonable risk to subjects enrolled in the study.

The DSMB will meet (in person or via telephone conference) a minimum of 3 times:

- after treatment of the first 4 subjects (2 in the TH arm and 2 in the control arm)

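### Primary endpoint 4 (potassium below 3.0 mEq/L) is sampled more often in the cooled arm and depends on unblinded cause attribution, so its between-arm comparison is confounded, in an uncertain direction

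*Combined protocol and SAP*

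**What the plan says.** - **Endpoint.** Endpoints, primary safety item 4, reads "Hypokalemia with potassium levels below 3.0mEq/L, not secondary to other identifiable causes". It carries no time window and no sampling rule.
- **Test.** Statistical Methods compares the primary endpoints between arms by a two-sample proportion test or Fisher's exact test, with a Bonferroni correction. It speaks of three dichotomous endpoints; Endpoints lists four.
- **Sampling in the cooled arm.** The Appendix 1 row "Potassium (pts randomized to cooling") is marked every 4 hours. The text on mitigating TH risks instead has "Serum electrolytes will be measured at regular intervals (every 4–6 hours"). Monitoring of Safety ties this monitoring to cooling: "Blood glucose and electrolyte measurements will be performed as per protocol for patients undergoing therapeutic hypothermia".
- **Sampling in both arms.** Appendix 1, note c, lists "serum lactate level, basic metabolic panel, hepatic function" and other tests at baseline, 18-24 h and 48-96 h. No other potassium draw is planned for controls. Further clinical draws are neither required nor ruled out.
- **Cause.** The TH risk section gives examples of other causes: "hypokalemia not due to other identifiable causes (diuretic administration, adrenal derangements, etc." Background says "Standard of care therapy for these patients involves initiation of ionotropes and/or vasopressors along with diuretics", and Procedures includes diuretics in the medical therapy of both groups. The same risk section says that cooling itself lowers potassium, by cellular shift and mild diuresis. It defines the matching adverse event only for patients undergoing TH.
- **Who decides.** Allocation is not blinded (Patient Population). The principal investigator assesses causality and the DSMB makes the final adjudication (Data Safety Monitoring Board section; DSMB Charter, section 2). Neither place says that adjudication is blind to arm.

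**The concern.** An endpoint that is met when a value crosses a threshold depends on how often the value is measured. With six scheduled draws in 24 hours of cooling against one in the same period for controls, equal risk need not give equal counts.

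The cause clause adds a second problem. A cooled patient on diuretics has two candidate explanations for a low potassium, and no rule specific to this endpoint chooses between them. A control has no cooling to attribute it to, so on a plain reading a control event counts only when nothing else explains it. People who know the arm make the judgement.

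The trial's stated purpose is safety, and the DSMB looks after 4 and after 10 subjects. A raw difference in this endpoint, or the lack of one, could be misread at either look or at the end.

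**Working it through.** **Plan's own figure.** The plan gives 20 patients (10 per arm) with no event rate, effect size or power, so there is nothing to reproduce. All rates, episode lengths and attribution shares below are assumptions.

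**Inputs from the documents.** 10 v 10 patients. Cooled-arm draws in 24 h: 24/4 = 6 (Appendix 1), or 24/6 = 4 at the long end of the text's range. Planned control draws after baseline in the first 24 h: 1. Two-sided alpha 0.05; Bonferroni 0.05/3 = 0.0167 or 0.05/4 = 0.0125.

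**Test.** Rejection probability = sum over all (a, b) of Bin(a; 10, p1) × Bin(b; 10, p2), where the two-sided Fisher p-value is at or below alpha. Against 0/10, Fisher needs 5/10 (p = 0.033) at 0.05 and 6/10 (p = 0.011) at either Bonferroni level. A result of 3/10 v 0/10 gives p = 0.21.

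**A. Sampling, one short episode.** Assume that 30% of patients in each arm have one 4-hour episode. Detection = episode length / draw interval, at most 1. Recorded share = 30% × detection.

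| Draws | Detection | Recorded | Expected of 10 | Rejection at 0.05, against 30% in cooled arm |
|---|---|---|---|---|
| Every 4 h (cooled) | 4/4 = 100% | 30% | 3.0 | – |
| Control, one draw | 4/24 = 17% | 5% | 0.5 | 9.3% |
| Control, every 6 h | 4/6 = 67% | 20% | 2.0 | 2.1% |

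For 30% v 5%, rejection is 2.9% at either Bonferroni level. If the control draw is placed at random in the 18-24 h window and the episode must fit within the 24 h, simulated detection is 13%, so 30% × 13% = 4% is recorded. A 12-hour episode is detected 100% v 25%. An episode that lasts all day is detected in both arms, and the gap is zero.

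**B. Sampling, independent draws (extreme case).** P(at least one low value) = 1 − (1 − p)^k, with the same per-draw risk p in both arms.

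| p | Cooled, k = 6 | Control, k = 1 | Rejection at 0.05 | At 0.0167 or 0.0125 |
|---|---|---|---|---|
| 0.02 | 11.4% | 2% | 0.2% | <0.1% |
| 0.05 | 26.5% | 5% | 6.0% | 1.6% |
| 0.10 | 46.9% | 10% | 24.5% | 12.1% |
| 0.20 | 73.8% | 20% | 50.2% | 30.8% |

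With k = 4 the cooled-arm shares are 7.8%, 18.5%, 34.4% and 59.0%. When both arms have the same number of draws (4 or 6, same p), rejection at 0.05 is 0.05% to 1.3%.

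**C. Attribution alone.** Counted share = true rate × (1 − share attributed to another cause).
- True 30% in both arms, 0% v 90% excluded: 30% × 1.0 = 30% v 30% × 0.1 = 3%. A difference is created (rejection 11.3% at 0.05).
- True 30% in both arms, 80% excluded in each: 30% × 0.2 = 6% v 6%. Most events disappear.
- True 40% v 20%, 50% v 0% excluded: 40% × 0.5 = 20% v 20% × 1.0 = 20%. A real difference is hidden.

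**D. Direction.** A and B push the cooled-arm count up. C can push either way. Repletion to stay above 3.5 mEq/L, stated in the TH section, could push the cooled-arm count down.

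**The case against.** The strongest case against has four parts.

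1. **Attribution is not a free judgement.** Table B of the DSMB Charter classes an event as related when an alternative cause is equally or less likely, so a tie between diuretic and cooling goes to the device. The DSMB, not the investigator alone, has the last word. This stands in part: it limits the loss of true TH events. But Table B governs adverse-event relatedness and is not expressly tied to endpoint 4, and no blinding is stated.
2. **The sizes rest on chosen inputs.** An episode as long as the cooled-arm interval gives 100% detection by construction. Routine clinical draws in controls would narrow the gap, and the 25% to 50% rejection rates need independent draws. This stands. At 30% v 5% the planned test rejects in under 10% of trials.
3. **It can be repaired from planned data.** Both arms have the same metabolic panels, and medications are recorded. A reader might infer that the bias cannot be undone; the documents do not support that. The plan does not, however, specify the repaired analysis.
4. **The exclusion concerns events.** A reader might infer that diuretic-treated patients drop out of the endpoint and that both arms would score zero. The wording excludes hypokalemia secondary to another cause. A patient on diuretics stays in and can have a counted event.

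What remains is that scheduled sampling differs by arm and that attribution is not stated to be blind.

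**Conclusion.** The concern holds as confounding of one primary endpoint, and it should be fixed. Followed as written, the plan compares arms on different numbers of scheduled draws and on a cause judgement made with the arm known or not stated to be hidden. It would go too far to say that the comparison carries no information on risk, or that the bias must run against cooling: risk, sampling and attribution are mixed, and the net direction is uncertain.

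The size cannot be fixed from the documents. Under equal assumed risk, the sampling effect ranges from nothing (persistent low potassium) through 30% v 5% recorded and about 9% rejection at 0.05 (one 4-hour episode, one control draw) to about 50% rejection (independent draws at 20% risk each). Unscheduled control draws shrink it.

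The conclusion assumes that endpoint 4 is among the primary endpoints tested; the count of three in Statistical Methods leaves this to be confirmed.

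**What to change.** - For the between-arm test, define endpoint 4 as any potassium below 3.0 mEq/L, regardless of cause, on the draws scheduled at the same times in both arms: the 18-24 h and 48-96 h panels.
- Use one clock for those panels. Appendix 1 counts from randomization, whereas Timing of Data Collection counts from the start and the completion of cooling, which controls do not have.
- Report the additional cooled-arm values, diuretic use and attributed cause descriptively, with cause preferably judged blind to arm.
- Reconcile the 4-6 hour interval in the TH risk text with the 4-hour interval in Appendix 1, and the three primary endpoints in Statistical Methods with the four listed under Endpoints.

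**Cost.** Protocol wording only; no added draws and no change to control monitoring. The price is fewer events in the formal comparison. In example A, the cooled-arm expectation over the first 24 h falls from 3.0 to about 0.5 of 10, equal to controls. The descriptive report keeps the remaining cooled-arm values in view. Extending the 4-hourly schedule to controls would also equalize sampling, but it changes their monitoring, may alter care, and is not needed.

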Appendix 2 – DSMB Charter

1. Introduction

This Charter is for the Data and Safety Monitoring Board (DSMB) for Cardiogenic Shock Intravascular Cooling Trial (CHILL-SHOCK). The DSMB will consist of a team of clinical researchers who are unaffiliated with this project. The members of the DSMB will not be investigators in this study and will be experienced in conducting and interpreting clinical trials. Their responsibilities will include reviewing the efficacy and safety endpoints at the set times points, as stated below. The Charter is intended to be a living document. The DSMB may wish to review it at regular intervals to determine whether any changes in the procedure are necessary.

2. Responsibilities of the DSMB

The DSMB is responsible for safeguarding the interests of study participants, assessing the safety and efficacy of study procedures, and for monitoring the overall conduct of the study.

The DSMB is an independent group advisory to the study PI and is required to provide recommendations about starting, continuing, and stopping the study. In addition, the DSMB is asked to make recommendations, as appropriate, to/about:

- Selection, recruitment, and retention of participants
- Adherence to protocol requirements
- Completeness, quality, and analysis of measurements
- Amendments to the study protocol and consent forms
- Confirmation of the PI's assessment of adverse events
- Final adjudication of all adverse events, as defined by *Table A* below
- Participant safety
- Notification of and referral for abnormal findings

3. DSMB Members

DSMB Chair: [name] University of Chicago Medicine Department of Medicine Section of Cardiology Assistant Professor of Medicine	[name], MSc Inova Health System Department of Medicine Section of Cardiology Professor of Medicine	[name] University of Chicago Medicine Department of Medicine Section of Cardiology Assistant Professor of Medicine
---------------------------------------------------------------------------------------------------------------------------------------------------------------------------	-----------------------------------------------------------------------------------------------------------------------------------------------	---------------------------------------------------------------------------------------------------------------------------------------------------

4. Scheduling, Timing, and Organization of Meetings: Data and Safety Monitoring Meetings

The DSMB will meet (in person or via telephone conference) a minimum of 3 times:

- after treatment of the first 4 subjects (2 in the TH arm and 2 in the control arm)
- after treatment of the first 10 subjects (5 in the TH arm and 5 in the control arm)
- at the conclusion of the study

The DSMB may convene additional meetings if necessary to ensure the ongoing monitoring and safety of the subjects treated with TH.

A quorum of at least two (2) DSMB members needs to be present for a meeting to commence. Members may either be present in person or have the option to phone-in if unable to arrive at the meeting location.

All DSMB members will receive an agenda prior to the meeting. In the event that a DSMB member is unable to attend a meeting, that member will receive minutes, as well as any additional notes, with the opportunity to share any additional thoughts on the distributed information.

5. Grading and Attribution Methods for Adverse Events

Grading Scale

The DSMB and the study team will utilize the Adverse Event Grading Scale provided in Table A. All adverse events will be graded according to this scale, the PI will prepare data regarding adverse events for review by the DSMB prior to meeting, and any additional details will be provided to the DSMB by the PI, as necessary.

Table A – Safety Reporting Definitions

Term	Definition
Adverse Event (AE) Ref: ISO 14155-2011 Ref: MEDDEV 2.7/3 12/2010	
Any untoward medical occurrence, unintended disease or injury, or any untoward clinical signs (including an abnormal laboratory finding) in subjects, users or other persons, whether or not related to the investigational medical device.
 
This definition includes events related to the procedures involved (any procedure in the clinical investigation plan).

Adverse Device Effect (ADE) Ref: ISO 14155-2011 Ref: MEDDEV 2.7/3 12/2010	
Adverse event related to the use of an investigational medical device
 
NOTE 1: This definition includes any adverse event resulting from insufficient or inadequate instructions for use, the deployment, the implantation, the installation, the operation, or any malfunction of the investigational medical device.
 
NOTE 2: This definition includes any event resulting from use error or from intentional misuse of the investigational medical device.

Serious Adverse Event (SAE) Ref: ISO 14155-2011 Ref: MEDDEV 2.7/3 12/2010	
Adverse event that:
 
• Led to death,• Led to serious deterioration in the health of the subject, that either resulted in:
○ a life-threatening illness or injury, or○ a permanent impairment of a body structure or a body function, or

Table A – Safety Reporting Definitions

Term	Definition
	
○ in-patient or prolonged hospitalization of existing hospitalization, or○ medical or surgical intervention to prevent life-threatening illness or injury or permanent impairment to a body structure or a body function● Led to fetal distress, fetal death, or a congenital abnormality or birth defect. 
NOTE: Planned hospitalization for a pre-existing condition, or a procedure required by the clinical investigational plan, without serious deterioration in health, is not considered a serious adverse event.

Serious Adverse Device Effect (SADE) Ref: ISO 14155-2011 Ref: MEDDEV 2.7/3 12/2010	Adverse device effect that has resulted in any of the consequences characteristic of a serious adverse event.
Unanticipated Adverse Device Effect (UADE) Ref: 21 CFR Part 812	Any serious adverse effect on health or safety or any life-threatening problem or death caused by, or associated with, a device, if that effect, problem, or death was not previously identified in nature, severity, or degree of incidence in the investigational plan or application (including a supplementary plan or application), or any other unanticipated serious problem associated with a device that relates to the rights, safety, or welfare of subjects.
Device Deficiency Ref: ISO 14155-2011 Ref: MEDDEV 2.7/3 12/2010	
A device deficiency is any inadequacy of a medical device with respect to its identity, quality, durability, reliability, safety or performance.
 
NOTE: Device deficiencies include malfunctions, misuse or use errors, and inadequate labeling.

Abbreviations: EC=Ethics Committee; IRB=Institutional Review Board

Underlying diseases are not reported as AEs unless there is an increase in severity or frequency during the course of the investigation.

Relationship to Study Device(s) and Reporting Requirements

The Investigator will assess the relationship of the AE to the study device as related or unrelated.

Table B – Criteria for Assessing Relationship of Study Device to Adverse Event

Classification	Description
Unrelated	The adverse event is determined to be due to a concurrent illness or effect of another device/drug and is not related to the investigational product.
Related	
• The adverse event is determined to be potentially related to the investigational product, and an alternative etiology is equally or less likely compared to the potential relationship to investigational product, or• There is a strong relationship to investigational product, or recurs on re-challenge, and another etiology is unlikely, or• There is no other reasonable medical explanation for the event.

Table C – Adverse Event Reporting

Event Classification	Event Recording	Communication to FDA	Communication to IRB
Adverse Event	
• Event reviewed and classified by PI• Event recorded in Oncore Adverse event database	Detail of all AE's will be given at time of annual report.	Details provided at time of annual review, per IRB policy.
Serious Adverse Event including Serious Adverse Device Effects	
• Event reviewed and classified by PI• Event recorded in Oncore Adverse event database	Reported via From 3500 within 48 hours of PI knowledge.	Details provided at time of annual review, per IRB policy (as these are not unanticipated events).
Unanticipated Adverse Device Effect / Unanticipated Serious Adverse Device Effect	
• Event reviewed and classified by PIStudy will be halted if event presents a significant or unreasonable risk to subjects enrolled in the study• Event recorded	Reported as soon as possible, but within 48 hours of PI knowledge, via From 3500.	UADE reported within 10 days of PI knowledge USADE reported directly to IRB Chairman upon PI knowledge, followed by formal reporting to the IRB within 48 hours. Study will be halted if event presents a

Table C – Adverse Event Reporting

Event Classification	Event Recording	Communication to FDA	Communication to IRB
	in Oncore Adverse event database		significant or unreasonable risk to subjects enrolled in the study

Device Deficiencies (including but not limited to failures, malfunctions, and product nonconformities)
 
Note: Any Investigational Device Deficiency that might have led to a serious adverse event if a) suitable action had not been taken or b) intervention had not been made or c) if circumstances had been less fortunate is considered a reportable event.
	
 Event reviewed and classified by PI Event recorded in Oncore Adverse event database 	
Investigational Device Deficiency that might have led to a serious adverse event if a) suitable action had not been taken or b) intervention had not been made or c) if circumstances had been less fortunate is considered a reportable event and will be reported to the FDA within 48 hours of PI knowledge, via Form 3500.
 
All other device deficiencies will be reported within 10 days.
	
Investigational Device Deficiency that might have led to a serious adverse event if a) suitable action had not been taken or b) intervention had not been made or c) if circumstances had been less fortunate is considered a reportable event will be reported to the IRB within 10 days of PI knowledge.

6. Example of Format for Minutes

Data and Safety Monitoring Meeting Minutes

Date:

Title of Protocol/IRB Number:

Principal Investigator/Designee:

Recommendations:

Continue the trial without modification

Accrual:

Recommend study be closed because of slow accrual
 Continue to monitor study, but consider closure because of slow accrual

Recommend study is amended/changed:

For patient safety reasons

- Rate of adverse events
- To extend accrual because of an event rate slower than expected

Other: _____

Signature of Principal Investigator: _____

Signature of DSMB Chair: _____

The DSMB will review adverse event data, other safety data, quality and completeness of study data, and enrollment data at each meeting to ensure proper trial conduct.

6. Reports of DSMB Deliberations and Reporting

Initial summary: The DSMB Chair is responsible for assuring the accuracy and transmission of a brief summary of the DSMB's discussion and recommendations to study PI and team within 7 days of the meeting or call. The study team will review this summary and either approve recommendation(s), or request additional information until agreement is reached.

Formal minutes: The DSMB Chair is responsible for the accuracy and transmission of the formal DSMB minutes for the Study PI within 30 days of the meeting or call. These minutes are prepared accordingly to summarize the key points of the discussion and debate (with the first priority being safety evaluation), requests for additional information, response of the investigators to previous recommendations, and the recommendations from the current meeting.
